8.1 Study Procedures

A series of clinical tests and procedures will be performed to assess toxicity and response throughout the study. The evaluations for this study will include:

- 1. Informed Consent each subject must sign a copy of the most current Institutional Review Board/Independent Ethics Committee (IRB/IEC) approved informed consent document. A copy of the signed document will be maintained with the subject's records.
- 2. Medical History past or current medical conditions, current medications, and medications taken within 30 days of study entry.
- 3. Surgical History A surgical history will be obtained by the Investigator or qualified designee. Surgical history will include all clinically relevant surgeries including, but not limited to artificial (prosthetic) joints, implants and/or devices, such as ports or stents. Surgical procedures that occur after study enrollment will be documented separately.
- 4. Prior Cancer History A prior cancer history will be obtained by the Investigator or qualified designee. The prior cancer history will include histological confirmation of cancer, tumor staging (refer to the most current American Joint Committee on Cancer Staging Manual, the fifth edition or higher), and prior cancer therapies and best response(s), if applicable.
- 5. Prior/Concomitant Therapies and Procedures- All prescription and nonprescription medication (excluding vitamins and nutritional supplements) taken by the subject from 28 days prior to signing informed consent and up to and including the completion of the 3-year *Lm* surveillance period will be recorded in the medical record and on the eCRF.
- 6. AEs/SAEs- The Investigator or qualified designee will assess each subject to evaluate for potential new or worsening AEs/SAEs from the time written informed consent is obtained through the completion of the 3-year *Lm* surveillance period of the study. AEs/SAEs experienced during this period will be reported and recorded in the eCRF. AEs will be graded and recorded throughout the study according to CTCAE v 4.03 (see Section 13.6). Toxicities will be characterized in terms regarding seriousness, causality, toxicity grading, and action taken with regard to study treatment.
- 7. Physical Examination evaluation by body system.
- 8. Vital Sign Measurements temperature, pulse, respiration rate, and blood pressure and weight will be taken pre-dose then every after each infusion of ADXS11-001. Weight will be taken pre-dose only. Height will be measured at screening only.

- 9. Prophylactic Medications The pretreatment prophylactic regimen will be administered prior to and be completed at least before each ADXS11-001 infusion as outlined in Section 11.1. Subjects may continue to receive NSAIDs doses and antiemetic administration per label or package insert, as needed following ADXS11-001 infusions
- 10. ECOG Performance Status Score according to the ECOG performance status criteria.
- 11. Hematology Profile a complete blood count (CBC) with differential, and platelet count.
- 12. Chemistry Profile glucose, total protein, albumin, uric acid, blood urea nitrogen (BUN), creatinine, lactic dehydrogenase (LDH), AST, ALT, alkaline phosphatase, total bilirubin, sodium, potassium, bicarbonate, chloride, and calcium.
- 13. Coagulation Profile international normalized ratio (INR) or prothrombin time (PT) and activated partial thromboplastin time (aPTT) will be assessed at screening only.
- 14. Urinalysis routine dipstick measurements and, if clinically indicated, microscopic analysis.
- 15. Urine Pregnancy Test A urine pregnancy test will be performed for all women of child bearing potential. A positive urine pregnancy test must be confirmed by a serum pregnancy test (minimum sensitivity 25 IU/L or equivalent units of βHCG).
- 16. Dispense/Prescribe Oral Prophylactic Antibiotics (1) During Study Treatment **Phase** - All subjects will receive a 7-day course of oral antibiotic therapy starting approximately 72 hours (Day 4) after administration of ADXS11-001. Antibiotic therapy should consist of either 160 mg trimethoprim/800 mg sulfamethoxazole (DS) tablet administered 3 times during the 7 consecutive days or 80 mg trimethoprim/400 mg sulfamethoxazole administered daily for 7 consecutive days or for subjects with sulfa allergy ampicillin 500 mg 4 times daily for 7 consecutive days may be administered. (2) Post Study Treatment - All subjects will receive a 6-month course of oral trimethoprim/sulfamethoxazole or ampicillin for subjects with sulfa allergy to be initiated approximately 72 hours following the last dose of study treatment or at the time of study discontinuation. The dose of trimethoprim/sulfamethoxazole consists of either 160 mg trimethoprim/800 mg sulfamethoxazole (DS) tablet administered 3 times a week or 80 mg trimethoprim/400 mg sulfamethoxazole administered daily. The dose of ampicillin consists of 500 mg 4 times daily for 6 months. Review the approved product labeling for Bactrim and ampicillin, and monitor antibiotic tolerance as dosing adjustments may be necessary.
- 17. Tumor Imaging—Computed tomography (CT) and magnetic resonance imaging (MRI) will be considered the best currently available and reproducible methods to measure target lesions (as defined in Section 9.1.4, Definition of Target/Non-target Lesions) selected for response assessment. Baseline tumor imaging/disease

assessment must be performed within 28 days prior to the first dose of study drug. Then imaging studies and tumor assessments will be performed every 12 weeks (\pm 1 week) after the initial ADXS11-001 infusion. Apparent progression within the first 12 weeks, not accompanied by clinical deterioration, should be confirmed \geq 4 weeks later. (See Section 9.1.12, Tumor Response).

- 18. Immune Monitoring The generation of E6 and E7 specific immune responses in the peripheral blood will be assessed by ELISpot or enzyme-linked immunosorbent assay (ELISA) based assays. Blood for immune monitoring will be collected immediately prior to every ADXS11-001 infusion and 2 weeks after each ADXS11-001 infusion in cycle 1 only (Day 1 of Weeks 1, 3, 4, 6, 7, 9, 10, and 12).
 - T cell ELISpot For blood collection, peripheral blood samples (around 50 mL total) will be withdrawn at the time points specified above. Whole blood will be processed over a Ficoll gradient to obtain PBMC, and PBMC will be washed, counted, aliquotted and frozen in dimethyl sulfoxide-containing freezing medium prior to long-term storage in liquid nitrogen. Sterile technique will be maintained throughout so that viable cells may be cultured and assayed after thawing. The peptide pools of E6 and E7 antigens for determination of immune responses will be provided by Advaxis.
- 19. Cytokines/Chemokines Blood for cytokine and chemokine analysis will be collected in Cycle 1 only at 3 time points immediately prior to each ADXS11-001 infusion and 2 hours and 4 hours post infusion (± 15 minutes) Day 1 of Weeks 1, 4, 7, and 10.

8.2 Screening Evaluations

All subjects must undergo Screening evaluations prior to the first ADXS11-001 infusion. Screening evaluations used to determine the subject's study eligibility must be completed within 28 days prior to the first ADXS11-001 infusion and include the following: histological confirmation of persistent, metastatic or recurrent squamous or non-squamous cell carcinoma, adenosquamous carcinoma, or adenocarcinoma of the cervix, tumor evaluations, medical history, prior and concomitant therapies; physical examination; vital sign measurements including weight, height (at Screening only); and ECOG Performance Status. Laboratory tests for Screening including hematology, coagulation, and chemistry profile; urinalysis; and a pregnancy test for women of childbearing potential must be performed within 28 days prior to the first dose of study treatment but maybe used as Cycle 1 Day 1 safety labs if done within 3 days of the first dose of study treatment. Screening/Baseline tumor evaluations must be performed 28 days prior to the first dose of study treatment.

Results of all screening evaluations must be reviewed by the principal Investigator or his/her designee to ensure that all eligibility criteria have been satisfied prior to subject

enrollment. Written informed consent must be obtained prior to the performance of any study specific Screening evaluations.

8.3 Study Cycle Evaluation

Baseline imaging studies and tumor assessments must be performed within 28 days prior to the first ADXS11-001 infusion in the first Treatment Period. Subsequent assessments will be conducted at Week 12 in Cycle 1, followed by assessment every 12 weeks (± 1 week) thereafter. Apparent progression within the first 12 weeks not accompanied by clinical deterioration, should be confirmed 3 to 4 weeks later.

Blood samples for immune monitoring and cytokine/chemokine analysis should be collected per schedule in Cycle 1 only (See Section 8.1 Study Procedures).

A physical examination, an ECOG Performance Status, vital sign measurements, hematology and chemistry profiles, and urinalysis will be performed prior to each study treatment infusion and at the end of therapy. Subjects will also be asked about the occurrence of any AEs and changes to concomitant medications.

Vital signs (including blood pressure, pulse rate, respiratory rate, and temperature) will be checked and recorded prior to administration of ADXS11-001 and following the infusion. Weight will be collected prior to each ADXS11-001 infusion.

A urine pregnancy test will be performed within 72 hours prior to each ADXS11-001 infusion and at the end of therapy for all women of childbearing potential.

8.4 End of Therapy Evaluations

End of therapy is not a visit. It is a list of assessments that must be completed upon the decision to discontinue a subject from study treatment. These evaluations include: a physical examination, ECOG Performance Status, vital sign measurements, weight, hematology, coagulation, and chemistry profiles, urinalysis, and imaging studies, if indicated. AEs and changes to concomitant medications will also be assessed and documented

8.5 Safety Follow-Up/Post-Treatment Visits

Safety follow-up will be conducted via a telephone call at 30 days (\pm 5 days) after the last ADXS11-001 infusion to confirm the resolution of any ongoing AEs and SAEs. Additional unscheduled visits may be considered as needed and at the discretion of the Investigator. Safety follow-up will also continue to be monitored for AEs and SAEs during the 3-year Lm surveillance period of the study (see below).

Surveillance monitoring for the detection of *Lm* will be initiated at the completion of study treatment according to the protocol or at the time of study discontinuation if earlier. This surveillance monitoring period will consist of a 6-month course of oral antibiotics,

obtaining a blood sample to monitor CBC, CMP, including CRP and ESR, and blood cultures at regular intervals. This testing will be performed on all subjects who have received at least 1 dose of ADXS11-001. It will occur every 3 months (±2 weeks) for 3 years beginning after the last dose of study treatment. If a persistent increase in CRP and/or ESR is observed with negative blood cultures for *Listeria* during this time, the subject should be evaluated and treated, as appropriate, for another possible cause. In the event that a definite cause has not been identified, subjects must continue to be monitored closely, including additional testing and a blood culture, for possible signs/symptoms of listeriosis. This testing may be performed at the investigational site or at another acceptable location following consultation with the Sponsor.

9 EVALUATION CRITERIA

9.1 Safety

The safety of ADXS11-001 administration will be assessed according to the NCI CTCAE v 4.03 criteria which will be used to define the grades and levels of toxicity. These criteria will be applied to:

- Observation of the infusion site for swelling, irritation, immune reaction or other abnormalities
- Changes from baseline in physical examination findings and vital signs
- Changes from baseline in laboratory parameters (hematology, coagulation, and serum chemistry)
- Evidence of allergic and constitutional symptoms
- Reported AEs

Safety evaluations will be performed throughout the duration of the study. All subjects who received at least 1 dose of ADXS11-001 will be evaluated for safety. See Section 13.2, Collection of Safety Information, for the definition of an AE.

9.1.1 Baseline Tumor Assessments

The baseline tumor burden (unidimensionally-measured or evaluable disease) will be assessed during the pretreatment evaluations. The Investigator will identify prospectively, the lesions to be followed in order to evaluate the subject's response to therapy (see Section 9.1.4, Definition of Target/Non-target Lesions). Imaging areas will include the chest, abdomen, pelvis and other areas as indicated by clinical presentation.

9.1.2 Tumor Imaging and Assessment of Disease

Computed tomography (CT) and magnetic resonance imaging (MRI) will be considered the best currently available and reproducible methods to measure target lesions (as

defined in Section 9.1.4, Definition of Target/Non-target Lesions) selected for response assessment. Conventional CT should be performed with contiguous cuts of 10 mm or less. Spiral CT scan should be performed using a 5 mm contiguous reconstruction algorithm (as a general rule, lesion diameter should be no less than double the slice thickness). Lesions on chest x-rays will be acceptable as measurable lesions when they are clearly defined and surrounded by aerated lung; however, CT is preferable. Ultrasound is not an acceptable method to measure disease.

Assessment of disease will be done using both RECIST 1.1 criteria and irRECIST criteria. All subjects who have completed one 12-week cycle of ADXS11-001 treatment will be considered evaluable for response.

9.1.3 Measurable and Non-Measurable Lesions and Disease

Measurable lesions will be those that can be accurately measured in at least one dimension with the longest diameter ≥ 2.0 cm (for spiral CT scan or MRI, ≥ 1.0 cm). Measurable disease will be present if the subject has one or more measurable lesions.

Non-measurable lesions/disease will be all other lesions (or sites of disease), including small lesions (those with all measurements < 2.0 cm or < 1.0 cm with spiral CT/MRI), or any of the following: bone lesions, leptomeningeal disease, ascites, pleural or pericardial effusion, inflammatory breast disease, lymphangitis, cutis/pulmonis, abdominal masses that are not confirmed and followed by imaging techniques, cystic lesions, and lesions occurring within a previously irradiated area unless they are documented as new lesions since the completion of radiation therapy.

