9.1.4 Target/Non-Target Lesions

All measurable lesions, up to a maximum of 2 lesions per organ and 5 lesions in total, should be identified as target lesions to be measured and recorded at baseline. The target lesions should be representative of all involved organs. Target lesions will be selected based on their size (the lesion with the longest diameter) and suitability for accurate repeated measurements. At baseline, a sum of the longest diameters for all target lesions will be calculated and recorded as the baseline tumor burden. The baseline sum will be used as the reference point to determine the objective tumor response of the target lesions.

Measurable lesions other than the target lesions and all sites of non-measurable disease will be identified as non-target lesions and will be recorded at baseline. Non-target lesions will be evaluated at the same assessment time points as target lesions.

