9.1.5 Response in Measurable Lesions (RECIST 1.1)

At baseline, the sum of the longest diameters (SumD) of all target lesions (up to 2 lesions per organ, up to 5 lesions total) is measured. At each subsequent tumor assessment, the SumD of the target lesions and of new, measurable lesions (≥10; up to 2 new lesions per

organ, total 5 new lesions) are added together to provide the total measurable tumor burden (TMTB):

TMTB = SumD target lesions + SumD new, measurable lesions

Percentage changes in TMTB per assessment time point describe the size and growth kinetics of both old and new measurable lesions as they appear. At each tumor assessment, the response in target and new measurable lesions is defined based on the change in TMTB.

- Complete Response (CR): Disappearance of all target lesions. Any pathological lymph nodes (whether target or non-target) must have reduction in short axis to <10 mm.
- Partial Response (PR): At least a 30% decrease in the sum of diameters of target lesions, taking as reference the baseline sum diameters.
- Progressive Disease (PD): At least a 20% increase in the sum of diameters of target lesions, taking as reference the smallest sum on study (this includes the baseline sum if that is the smallest on study). In addition to the relative increase of 20%, the sum must also demonstrate an absolute increase of at least 5 mm. (Note: the appearance of one or more new lesions is also considered progression).
- Stable Disease (SD): Neither sufficient shrinkage to qualify for PR nor sufficient increase to qualify for PD, taking as reference the smallest sum diameters while on study.

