9.1.6 Immune-Related Response in Measurable Lesions (irRECIST)

In addition to evaluation using RECIST 1.1 criteria, an immune response adaptation of RECIST will be applied to this trial. The essential differences between irRECIST and RECIST criteria are as follows:

- New measureable lesions do not necessarily constitute progressive disease and they should be added into the total tumor burden. New non-measurable lesions do not constitute disease progression but will prevent the determination of an irCR.
- Apparent disease progression should be confirmed after 4 weeks in the absence of symptoms consistent with clinical deterioration.

At baseline, the sum of the longest diameters (SumD) of all target lesions (up to 2 lesions per organ, up to total 5 lesions) is measured. At each subsequent tumor assessment (TA), the SumD of the target lesions and of new, measurable lesions (\geq 10 mm [lymph nodes \geq 15 mm in shortest diameter]; up to 2 new lesions per organ, total 5 new lesions) are added together to provide the total measurable tumor burden (TMTB):

TMTB = SumD target lesions + SumD new, measurable lesions

Percentage changes in TMTB per assessment time point describe the size and growth kinetics of both old and new, measurable lesions as they appear. At each tumor assessment, the response in target and new, measurable lesions is defined based on the change in TMTB (after ruling out irPD) as follows:

- Complete Response (irCR): complete disappearance of all target and new, measurable lesions, with the exceptions of lymph nodes which must decrease to <10 mm in short axis
- Partial Response (irPR): decrease in TMTB ≥30% relative to baseline (see below)
- Stable Disease (irSD): not meeting criteria for irCR or irPR, in absence of irPD
- Progressive Disease (irPD): increase in TMTB ≥20% relative to nadir

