9.1.9 Overall Response

Overall response will be determined based on RECIST 1.1 criteria and by irRECIST criteria (Table 6). Overall response according to irRECIST is derived from the responses in measurable lesions (based on TMTB) and the presence of any non-measurable lesions.

Table 6 Tumor Response Evaluation: Comparison of RECIST 1.1 and irRECIST

Criteria	RECIST 1.1	irRECIST
New measurable lesions (≥ 10 mm)	Always represents PD	Incorporated into tumor burden
New non- measurable lesions (< 10 mm)	Always represents PD	Does not define progression but precludes irCR
Non-Target lesions	Changes contribute to defining BOR of CR, PR, SD, and PD	Contribute to defining irCR (complete disappearance required)
CR	Disappearance of all lesions	Disappearance of all lesions
PR	≥ 30% decrease in the sum of the longest diameter of all target lesions compared with baseline, in absence of new lesions or unequivocal progression of non-target lesions	≥ 30% decrease in tumor burden compared with baseline

Criteria	RECIST 1.1	irRECIST
SD	Neither sufficient shrinkage to qualify for PR nor sufficient increase to qualify for PD, taking as reference the smallest sum diameters while on study	Neither a 30% decrease in tumor burden compared with baseline nor a 20% increase compared with nadir can be established
PD	At least 20% increase in sum of diameters of target lesions, taking as reference the smallest sum on study. In addition to the relative increase of 20%, the sum must also demonstrate an absolute increase of at least 5mm. The appearance of one or more new lesions is also considered progression.	At least 20% increase in tumor burden compared with nadir (at any single time point) ^a

irRECIST = immune-related Response Evaluation Criteria in Solid Tumors; BOR = best overall response; CR = complete response; irCR = immune-related complete response; PD = progressive disease; PR = partial response; SD = stable disease;

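### Baseline lymph nodes are selected and summed by longest diameter but assessed for complete response by short axis, and no section reconciles the two

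*Combined protocol and SAP*

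**What the plan says.** **Longest diameter.** Section 9.1.3 makes a lesion measurable if it can be "accurately measured in at least one dimension with the longest diameter ≥ 2.0 cm (for spiral CT scan or MRI, ≥ 1.0 cm"). Nodes get no rule of their own. Section 9.1.4 continues on that axis: "Target lesions will be selected based on their size (the lesion with the longest diameter"), and "a sum of the longest diameters for all target lesions will be calculated and recorded as the baseline tumor burden". Sections 9.1.5 and 9.1.6 repeat a longest-diameter sum. For PR, the bullet in 9.1.5 asks for "At least a 30% decrease in the sum of diameters of target lesions, taking as reference the baseline sum diameters" without naming an axis, while the RECIST 1.1 column of Table 6 (Section 9.1.9) asks for a "30% decrease in the sum of the longest diameter of all target lesions compared with baseline".

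**Short axis.** For CR, 9.1.5 says "Any pathological lymph nodes (whether target or non-target) must have reduction in short axis to <10 mm". For irCR, 9.1.6 requires all target and new measurable lesions to be gone, "with the exceptions of lymph nodes which must decrease to <10 mm in short axis". Section 9.1.7 treats a node below 10 mm short axis as non-pathological. Section 9.1.6 counts a new node as measurable only from "15 mm in shortest diameter".

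**Neither.** Table 6 defines CR under both criteria as every lesion gone, with no allowance for a small residual node. Section 9.1.8 and Tables 6 and 8 treat lesions as measurable from 10 mm, also without a nodal exception.

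**The concern.** A baseline node enters the sum on its long axis, leaves disease on its short axis, and, if it is new under irRECIST, must pass a third limit. Nodes rarely shrink in equal proportion on both axes, so the category a subject receives can depend on which sentence the assessor followed.

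At stake are the response category under both criteria and the ORR, which Section 14.5.5 builds from CR/irCR and PR/irPR. CR status also has a consequence beyond the tables: the Synopsis and Section 6 end treatment one cycle after a CR. An unclear CR definition therefore reaches a treatment rule, and the sections must be reconciled for that reason too.

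**Working it through.** The plan contains no figure to reproduce on this point. The check applies its own limits to single nodes, written as longest diameter x short axis. The node sizes are illustrative assumptions, imaging is spiral CT or MRI, and the change is (follow-up - baseline) / baseline.

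**1. Status of a small node, 12 x 8 mm.**
- Longest diameter 12 mm is at least 10 mm, so 9.1.3 makes it measurable and 9.1.4 allows it as a target.
- Short axis 8 mm is below 10 mm, so 9.1.7 calls that size non-pathological.
- If the same node appeared later, 9.1.6 would not count it as measurable (8 mm is below 15 mm). Table 6, read with the longest-diameter rule of 9.1.3, would (12 mm is at least 10 mm).

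**2. Under-called response, sole target node 24 x 16 to 18 x 11 mm.**
- Longest-diameter sum, as the plan states it: (18 - 24) / 24 = -25%. This is short of the 30% fall for PR, so SD.
- Short axis: (11 - 16) / 16 = -31.25%. This would be PR.
- At 11 mm the node is not below 10 mm, so the nodal CR clause does not apply and cannot rescue the SD call.

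**3. Conflict between the sum and the CR clause, 24 x 16 to 18 x 9 mm.**
- Longest-diameter sum: again (18 - 24) / 24 = -25%, so SD.
- Short axis 9 mm is below 10 mm, so the nodal CR limit of 9.1.5 is met.
- Table 6 taken literally refuses CR, because the node is still there.

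**4. Weight of one subject.** The effect on ORR is 1/n. Section 6 plans about 15 subjects treated at the RP2D. Section 14.5 limits the efficacy population to those who complete at least one cycle, so n may be smaller.

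| n | 1/n |
|---|---|
| 15 | 6.7 points |
| 12 | 8.3 points |
| 6 | 16.7 points |

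Only a case like step 2 changes ORR when every clause is applied. In step 3 an assessor who applies the nodal clause records CR, and so would one using short axis throughout. ORR moves there only if the assessor follows the sum or Table 6 instead.

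**The case against.** Several points on the other side are sound.

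- **One nodal change yields SD, PR or CR.** A reader might infer that the text allows all three. It does not. PR on short axis needs a short-axis sum, and 9.1.4 to 9.1.6 and Table 6 all use longest diameter. The unnamed axis in the PR bullet of 9.1.5 is loose wording inside a section that opens with a longest-diameter sum. What the text yields is SD against CR. The PR result in step 2 shows what the stated rule misses.
- **A node below 10 mm at baseline already satisfies CR.** This is also tempting, but 9.1.5 requires a reduction in pathological nodes and 9.1.6 requires a decrease. An unchanged 12 x 8 mm node shows neither. What remains is that the plan can make a target of a node it calls non-pathological.
- **Subjects could enter improperly.** Inclusion criterion 4 accepts evaluable disease as an alternative to measurable disease, so reclassifying a small node need not change eligibility.
- **The 15 mm limit is a third rule everywhere.** It stands only in 9.1.6. Under RECIST 1.1, any new lesion is progression whatever its size.
- **irRECIST resolves itself.** Section 9.1.6 defines irSD as meeting neither irCR nor irPR, so on that section alone a node below 10 mm gives irCR. Table 6 reopens the question by requiring every lesion to be gone.

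It can also be said that naming RECIST 1.1 is enough. That does not help, because the protocol writes out its own selection and sum rules, and an assessor who follows them measures the long axis of nodes. The availability of radiographs for independent review (Section 15.4) makes a re-read possible but gives the re-reader no rule.

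**Conclusion.** The concern holds. The plan selects and sums baseline nodes on longest diameter and assesses nodal CR on short axis, and nothing in the documents brings the two together. Followed as written, it can under-call nodal shrinkage (SD at -25% where the short axis fell 31%) and can give SD and CR for the same scan. A change mainly in the long axis would err in the opposite direction.

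The weight is moderate. Tumor response is a secondary, descriptive endpoint with no test or decision threshold attached. The 6.7 points at an assumed n = 15 is the weight of any one reclassified subject. It is not an estimate of bias, since the documents do not say how many subjects will have nodal targets or what shapes those nodes have. No effect on PFS has been worked out, and none is claimed. The link from CR to the end of treatment is the main reason to settle the definition before data are read.

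**What to change.** In 9.1.3 to 9.1.6, 9.1.8 and Tables 6 and 8:

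1. Measure nodes on the short axis at every time point, the axis already used for CR and for new irRECIST nodes.
2. Define the sum as longest diameter for non-nodal lesions plus short axis for nodes, and name the axis in the PR and PD definitions.
3. Apply one nodal target threshold to baseline and new nodes: the protocol's own 15 mm short-axis limit. Nodes of 10 to <15 mm are then non-target, and nodes below 10 mm are normal. Carrying the 15 mm limit over to baseline nodes is a choice that the sponsor should state, because 9.1.6 now applies it to new nodes only.
4. State in Table 6 that CR and irCR allow residual nodes below 10 mm short axis, so the sum may be non-zero.

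With these rules, 24 x 16 to 18 x 11 mm is PR, 24 x 16 to 18 x 9 mm is CR with a remaining sum of 9 mm, and a 12 x 8 mm node is never a target.

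The cost is protocol wording and the lesion eCRF page; scans and readers stay the same. A few subjects with only small nodes will become non-measurable but remain evaluable, which inclusion criterion 4 permits.
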